6.2 Visit 2 (12-84 hours) - Hospital

This visit is optional, and would be timed within 12-84 hours of etanercept administration. If the intravenous line is still in place, or a blood draw is clinically indicated within this window, approximately 4 cc of blood is drawn for the PK test. A numbing agent may be used to decrease the discomfort associated with phlebotomy. The blood is sent to the laboratory for the necessary blood work. Patients are generally observed for 24 to 48 hours after completion of IVIG dose prior to discharge. Study investigators will observe patients through that period in the hospital. Observation will continue if patient hospitalization extends beyond that period for complications of disease or therapy until the patient is discharged.

CONFIDENTIAL

This material is the property of the Seattle Children's Research Institute. Do not disclose or use except as authorized in writing by the study sponsor-investigator.

6.3 Visit 3 (Day 7 ± 72 hours)- Clinic

A physical assessment and a blood draw (approximately 7 cc) are required. A nurse may perform an abbreviated physical exam as part of the nursing assessment, since a physician investigator is not required to be present at this visit. A numbing agent may be used to decrease the discomfort associated with phlebotomy and/or study drug administration. The blood sample is sent to the laboratory for the tests listed in the study schema, while study personnel will process the PK sample and store for later shipping. A nurse administers a subcutaneous injection of study medication at the appropriate dosage.

6.4 Visit 4 (Day 14 ± 72 hours)- Clinic

A physical exam and a blood draw (approximately 7 cc) are required. A numbing agent may be used to decrease the discomfort associated with phlebotomy or study drug administration. The blood sample is sent to the laboratory for the tests listed in the schema while study personnel will process the PK sample and store for later shipping. An Echo and EKG are performed. A nurse administers a subcutaneous injection of study drug at the appropriate dosage.

6.5 Visit 5 (Day 44 ± 4 days)- Clinic

A physical exam and a blood draw (approximately 7 cc) are required. . The blood sample is sent to the laboratory for the tests listed in schema. An Echo/ EKG is performed. No study drug is administered.

6.6 Treatment for refractoriness to IVIG.

All patients who fit the requirements for refractoriness to IVIG (see section 3.1) will receive standard clinical treatment as determined by the attending physician. Standard treatment is usually a second dose of IVIG, and is defined in the American Heart Association guidelines. Retreatment with IVIG will not interrupt the study and study medication should still be administered.

6.6 Follow-up Echocardiogram Surveillance

Follow up data will be collected for patients who had a positive echo (z score ≥ 2.5 or aneurysm) at visit 5 for 14 months following their diagnosis or until their echo normalizes. De-identified visit notes and echocardiogram and angiogram reports that fall within this window should be sent to the study sponsor.

6.7 Echocardiography

In order to maintain consistency with other U.S clinical trials in KD¹⁷, coronary artery dimensions will be normalized for body surface area as z scores (SDs from a predicted normal mean). Coronary artery Z-scores are based on nonlinear regression equations derived from a normal nonfebrile population, comprised of 221 healthy children aged 0 to 18 years seen in the noninvasive laboratory at Boston Children's Hospital for echocardiographic evaluation during the years 1987 to 2000⁵⁵. These patients had no evidence of structural or functional heart disease. Z-scores algorithms are available and will be determined for the left main coronary artery, proximal left anterior descending, and proximal right coronary artery

$$\text{LMCA} = 0.31747 \cdot (\text{BSA}^{0.36008}) - 0.02887, \text{ SD} = 0.03040 + (0.01514 \cdot \text{BSA})$$

$$\text{pLAD} = 0.26108 \cdot (\text{BSA}^{0.37893}) - 0.02852, \text{ SD} = 0.01465 + (0.01996 \cdot \text{BSA})$$

$$\text{pRCA} = 0.26117 \cdot (\text{BSA}^{0.39992}) - 0.02756, \text{ SD} = 0.02407 + (0.01597 \cdot \text{BSA})$$

where LMCA indicates left main coronary artery, in centimeters; pLAD, proximal anterior descending coronary artery, in centimeters; pRCA, proximal right coronary artery, in centimeters; and BSA, body surface area, in meters squared calculated by the Haycock method⁵⁵.

In order to limit interobserver variability, a central Echocardiography reader will adjudicate these interpretations. Presence of coronary artery aneurysms will be determined using Japanese Ministry of Health Criteria: aneurysm diameter \geq 1.5 times the diameter of the vessel immediately proximal. All centers will forward digital echocardiograms to the Seattle Center for central reading by a single observer. [name] is a Boston trained Pediatric Cardiologist and spent an extra year in an imaging fellowship, prior to taking a faculty position at CHRMC-UW. He is intimately familiar with procedures used to develop z-scores from the cohort of patients at Boston Children's and will provide consistency for the echo determinations.

6.8 **Pharmacy Procedures**

The pharmacist and pharmacy technical staff will be not be blinded. The study statistician will provide each site pharmacy with randomization table. Pharmacists will supply each patient with drug or placebo, both provided by Amgen in separate labeled vials. Pharmacists will draw dose in syringes and dispense to nursing for administration. Drug accountability will be monitored by the CRO as described below. Study randomization codes and links to patients will be kept in secure records in pharmacy. All other study personnel involved in administration of drug will be blinded.

6.9 **IVIG Retreatment**

As noted in section 3.1: The primary aim of this study is to determine if Etanercept (Enbrel) 0.8 mg/kg given subcutaneously to patients with acute Kawasaki Disease will reduce the incidence of IVIG refractoriness as defined in the joint American Heart Association and American Academy of Pediatrics Endorsed Clinical Report: "Refractory Kawasaki Disease will be defined as the persistence or recrudescence of fever ($\geq 38.0^{\circ}\text{C}$ or 100.4°F) at least 36 hours after the end of the IVIG infusion"³. Persistent or recrudescent fever is the sole criteria for determining the need for retreatment. The clinical decision can be supported by persistent symptoms and persistent elevation or rebound of inflammatory parameters such as CRP. The protocol requires waiting at least 36 hours after completing the first IVIG dose before initiating the second dose.

7 Statistical Design and Analysis

The primary outcome variable is the Y/N determination of whether the subject is refractory to IVIG treatment, defined as persistence of fever $>38^{\circ}\text{C}$ beyond 36 hours from completion of IVIG treatment, or recurrence of fever within 10 days, and clinical decision to retreat with IVIG. Chi-square testing will be used to compare the proportions of subjects classified as refractory to IVIG treatment between the group randomized to receive Etanercept as an adjunctive therapy and the group randomized to receive placebo. If necessary (due to low cell counts), a Fisher's Exact test can be substituted. Stratified versions of the chi-square and Fisher's tests are available in StatXact (Cytel Incorporated) to allow stratification by center.

Secondary outcome variables that are measured on a continuous scale include the coronary artery diameters obtained on the LMCA, pLAD and pRCA and the corresponding Z-scores (normalized for the patient's BSA) at each of those locations. Z-scores will be summarized at each time point by treatment group and the within-subject changes in Z-score relative to baseline will be summarized for the post-treatment time points (week 1 and week 5) as well. The within-subject changes in actual artery diameter will also be summarized at week 1 and week 5. Summary statistics will include the mean, SD and selected percentiles.

CONFIDENTIAL

This material is the property of the Seattle Children's Research Institute. Do not disclose or use except as authorized in writing by the study sponsor-investigator.

Change values will be summarized both overall for the treatment group as a whole and then stratified by whether or not the subject has evidence of dilation at baseline (Z -score ≥ 2.5). A Generalized Estimating Equation (GEE) model will be used to compare change values between the Etanercept and placebo groups. The GEE model is needed to accommodate adjustment for the correlation between observations obtained on the same individual at 1 and 5 weeks. Since the addition of Etanercept may have a differing magnitude of impact on change in artery diameter depending on whether the artery was dilated at baseline, terms for dilation status at baseline and the interaction between dilation and treatment group will be included in the model.

Another secondary outcome is the presence of aneurysm as defined by the Japanese Health Ministry criteria (see Echo criteria above). The pre- and post-treatment proportions of subjects in each group having an aneurysm detected will be calculated along with the exact binomial 95% confidence interval. Comparison of post-treatment aneurysm proportions will be done via a stratified Chi-square test, with strata for presence/absence of aneurysm at baseline.

Adverse events will be tabulated for each treatment group by severity, relationship to study drug and body system affected (according to the NCI CTC grading and MEDDRA classification system). The outcome of any SAE episodes that occur will be summarized. Adverse event rates will be compared between treatment groups using Poisson or negative binomial regression modeling. The proportions of subjects experiencing an adverse event of any type and the proportions experiencing an SAE will be compared using chi-square or Fisher's Exact testing.

Pharmacokinetic analyses: PK analyses will be performed after completion of the study and unblinding, so as not to unblind study investigators. Samples from patients receiving etanercept will be forwarded to the Seattle site for storage and then later submitted to Amgen for determination of serum drug concentrations. Peak and trough analyses will be performed. Drug clearance, volume of distribution and $\frac{1}{2}$ life will be determined using etanercept modeling and algorithms⁴¹ and loaded on SAAM2 software available at the University of Washington.

CRP and other standard laboratory studies will be performed in the clinical laboratory of each participating hospital. Serum cytokines, IL-3, IL-6, and TNF α will be performed in Center of Developmental Therapeutics at Children's Hospital Research Institute in Seattle. Assay will be performed on Luminex-200 multiplex system, which resides in center.

8 Safety and Adverse Events

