5.7.4 Return or Destruction of Study Drug

Study drug that remains at the end of the study will be shipped back to Amgen, Inc or destroyed on site.

At the completion of the study, there will be a final reconciliation of drug shipped, drug consumed, and drug remaining. This reconciliation will be logged on the drug reconciliation form, signed and dated. Any discrepancies noted will be investigated, resolved, and documented prior to return or destruction of unused study drug. Drug destroyed on site will be documented in the study files.

6 Study Procedures

Etanercept 0.8mg/kg (maximum 50 mg) or placebo will be given within 48 hours of initiating IVIG infusion. Randomization will be performed by internal Pharmacy, unblinded (see Pharmacy procedures). Placebo format

CONFIDENTIAL

This material is the property of the Seattle Children's Research Institute. Do not disclose or use except as authorized in writing by the study sponsor-investigator.

will be: Etanercept placebo (Amgen), TMS Lyo, B20 UnLBL 2mL vial Pink Cap. Study schema and procedures are outlined below.

TIME	0*	12-84 hours #	7 ± 3 days	14 ± 3 days	44 ± 4 days
Physical Exam	x		x	x	X
Etanercept/Placebo	x		x	x	
PK	x	x	x	X	
Cytokines	x	x	x		
CBC^	x		x	x	X
CRP	x		x	x	X
ESR	x				
Echo	x			x	X
EKG	x			x	X
AST, ALT	x		x	x	
Albumin	x		x	x	X

* Time 0 or baseline is defined as time first dose of study drug is given. Time 0 or baseline labs are almost always done before the patient has consented to the study. These labs are optional unless the patient is qualifying into the study through supplementary lab data. In general, admission laboratory values used to confirm diagnosis of KD can be used for the study, provided that they were within 24 hours prior to initiating IVIG. If a time zero lab value is not drawn as part of the clinical course prior to the patient enrolling in the study, it will not be collected and will be recorded as missing data. After enrollment, coordinators should try to retrieve extra serum obtained along with admission laboratory studies. This serum can be used for baseline pharmacokinetic assay, PK.

An EKG is normally done at time zero as part of clinical care. This EKG is optional, if an EKG is not performed at baseline it will not be recorded as a protocol deviation.

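### Does the primary chi-square test need a fixed decision on stratification by centre?

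*Combined protocol and SAP*

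**What the plan says.** Section 7 is the only place that defines the primary test. It has three parts:

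- a commitment: "Chi-square testing will be used to compare the proportions of subjects classified as refractory to IVIG treatment";
- a permission: "If necessary (due to low cell counts), a Fisher's Exact test can be substituted", with no numerical trigger;
- a remark about software: "Stratified versions of the chi-square and Fisher's tests are available in StatXact (Cytel Incorporated) to allow stratification by center".

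For aneurysm, a secondary outcome, the same section is firmer: the comparison "will be done via a stratified Chi-square test, with strata for presence/absence of aneurysm at baseline". Those strata are baseline aneurysm status, not centre.

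On allocation, Section 6 says "Randomization will be performed by internal Pharmacy, unblinded", and Section 6.8 says "The study statistician will provide each site pharmacy with randomization table". Neither says whether the site lists are blocked. Section 4.3 sizes the trial on two simple proportions and does not bring in centre.

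**The concern.** The primary P value should come from one test named in advance. Here the wording could support a plain or a centre-stratified test, each with a Fisher-type alternative, so there are four candidates. A secondary outcome is specified more tightly than the primary one. If someone looked at both results and reported the better one, the false-positive rate would exceed its nominal level.

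There is also an efficiency question. Part of the primary outcome is a clinical decision to retreat, so failure rates may differ between sites. A plain test then ignores chance imbalance between arms within sites. If the lists are blocked by site, it is also somewhat conservative.

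**Working it through.** **1. The plan's own figure.** Section 4.3 gives 110 per group for 25% versus 10% at 80% power. Alpha is not stated there; two-sided 0.05 is assumed.

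- Without continuity correction: n = [1.96·√(2·0.175·0.825) + 0.8416·√(0.25·0.75 + 0.10·0.90)]² / 0.15² = (1.0532 + 0.4433)² / 0.0225 = 99.5, so 100.
- With correction: (99.5/4)·[1 + √(1 + 4/(99.5·0.15))]² = 112.5, so 113, close to the stated 110.
- The other three rows (270, 59, 42) reproduce exactly with the correction.

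The sample size therefore rests on an unstratified comparison of two proportions.

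**2. Does the Fisher option matter?** With 98 per arm (196/2) and 25% versus 10%, the expected number of failures per arm is 98 × 0.175 = 17.2. For this to fall below the conventional 5, the overall failure rate would have to be under 5/98 = 5.1%. For the plain two-by-two table, the substitution is very unlikely to be triggered.

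**3. Plain chi-square against CMH.** The simulation used:

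- from the documents: 196 patients, the 8 sites listed in the Study Summary, 25% control failure and 10% under treatment;
- assumed: equal site sizes (24 or 25), a common odds ratio, and four patterns of site control rates;
- two-sided 0.05, no continuity correction, 25% in both arms under the null;
- 400,000 null and 200,000 alternative runs per case.

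The either column is the chance that at least one of the two tests is significant under the null. The last column, the share of null trials in which the verdicts differ, is 2 × either − plain − CMH.

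| Lists | Site control rates | Null: plain | Null: CMH | Null: either | Power: plain | Power: CMH | Null verdicts differ |
|---|---|---|---|---|---|---|---|
| Blocks of 4 | all 25% | .0508 | .0499 | .0519 | .806 | .804 | 0.3% |
| Blocks of 4 | 13–37%, linear | .0466 | .0494 | .0503 | .809 | .813 | 0.5% |
| Blocks of 4 | half 13%, half 37% | .0424 | .0498 | .0501 | .813 | .826 | 0.8% |
| Blocks of 4 | 5–45% | .0407 | .0499 | .0501 | .813 | .829 | 1.0% |
| Unblocked | all 25% | .0508 | .0497 | .0586 | .804 | .787 | 1.7% |
| Unblocked | 13–37%, linear | .0506 | .0495 | .0621 | .803 | .795 | 2.4% |
| Unblocked | half 13%, half 37% | .0511 | .0502 | .0660 | .804 | .809 | 3.1% |
| Unblocked | 5–45% | .0513 | .0501 | .0668 | .805 | .814 | 3.2% |

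A separate run of these eight cases agreed to within simulation error.

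**4. Other settings.**

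- Unequal site sizes (10 to 50 patients), 5–45%, unblocked: either test significant .0677.
- Five sites: .056 to .068 unblocked, .050 to .052 blocked.
- Across both eight-site layouts, CMH power minus plain power runs from −1.8 points (sites alike, unblocked) to +1.8 points (5–45%, blocked).
- Under 25% versus 10%, the verdicts differ in 0.7–1.9% of trials with blocked lists and 4.5–7.4% with unblocked lists.
- The pairing of 196 patients with 25% versus 10% matches neither table in Section 4.3. At 196 with 25% versus 8%, the verdicts differ in about 0.4–0.9% (blocked) and 2.8–3.8% (unblocked). At 220 with 25% versus 10%, they differ in about 0.6–1.3% and 3.5–5.7%.

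**The case for a change.** The strongest case for a change is textual. If the plain test is the default, the StatXact sentence seems to have no purpose. If stratification is intended, the text never commits to it. Two careful statisticians could report different primary P values and both claim to follow the plan. The protocol's committee reporting adds to this: under Sections 10.4 and 10.6, Session Reports go to everyone attending the DMC meeting and include analyses of the primary endpoint. Whether these are shown by arm is not stated. Site differences are also plausible: the background and Section 4.3 cite refractory or retreatment figures of 13%, 23% and 26%, under differing definitions.

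It stands that the text is not conclusive. The rest carries less weight. The mandatory wording attaches to chi-square testing, while the stratified and Fisher options are permissive. The aneurysm paragraph shows that the authors state stratification outright when they intend it. Section 4.3 is consistent with a plain comparison. Nothing in the documents says that the test will be chosen after results are known or that the lists are unblocked.

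**Conclusion.** This is a gap that analysts fill sensibly, and no change to the plan follows. Choosing either test without reference to the results gives a sound primary analysis. CMH holds its size at about 0.050. The plain test is at about 0.051 or, with blocked lists and differing sites, on the conservative side (down to 0.039 across the layouts run).

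The inflation to about 0.059–0.068 needs two conditions together, unblocked lists and selection after seeing the results, and its upper end also needs site rates assumed at 5–45%. With blocked lists, choosing the better result leaves the rate at 0.050–0.052.

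Making the stratified test mandatory brings no clear gain. It could cost or add up to about 1.8 points of power, and the sign depends on blocking and on site differences that the documents do not give. Naming the plain test would remove the ambiguity equally well, so the concern does not favour one test over the other. These sizes rest on the assumed site numbers, site sizes and site rates, and on two-sided 0.05.

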We will test the hypothesis that TNF- α antagonism with etanercept improves the clinical response to standard of care treatment with IVIG and aspirin therapy in KD patients between 2 months and 20 years of age. To test this hypothesis we will perform a double-blinded placebo controlled trial in 196 children with KD and obtain data in order to achieve an orphan designation for etanercept.

Primary Aim

1. Determine if etanercept (0.8 mg/kg, maximum 50 mg) given subcutaneously reduces IVIG refractory rate and retreatment rate in the KD patient population. Our goal is to randomize and complete the trial in 110 patients in the etanercept treatment group and 110 patients in the placebo group.

Secondary Aims

1. Determine if the safety profile differs between the etanercept treated group and the placebo group.
2. Determine if etanercept treatment alters the rate of coronary artery dilation and disease (CAD) defined by z-scores at 2 and 6 weeks after treatment.
3. Determine the pharmacokinetics of etanercept in KD patients

3 Research Design and Methods

We propose a placebo-controlled randomized double blind multi-center study in patients, age 2 months to 20 years, with acute Kawasaki disease. All study investigators will be blinded except for pharmacists.

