3.2 Secondary Clinical Endpoints

Determine if the safety profile differs between the etanercept treated group and the placebo group.

Secondary safety endpoints will be number of adverse events, serious or otherwise within 30 days of treatment, with specific focus on serious infections, defined as “those requiring hospital admission” for treatment. The latter have been noted in patients receiving much longer courses of etanercept than proposed for this protocol, and for different diseases.

Our study will be the first to evaluate efficacy of Etanercept in reducing inflammation in an acute inflammatory disease in children, as opposed to chronic inflammatory diseases. The acute phase reactant, C-reactive protein, will be followed throughout the study as a laboratory measure of inflammation. We will also determine if etanercept modifies serum concentrations of cytokines, interleukin-3, interleukin-6, and TNF- α .

We propose the largest cohort for study of Etanercept in children performed to date.

Secondary clinical endpoints will be directed to determine if etanercept treatment alters the rate of coronary artery disease defined by z-scores at 2 and 6 weeks after treatment.

We will also determine if etanercept treatment 1) alters development of coronary artery dilation or disease in patients with normal coronaries on initial echocardiogram, 2) promotes healing of coronary artery disease, when apparent on initial echocardiogram, 3) alters treatment course by reducing total number of hospitalization days, and 4) incidence of CRP normalization by 7 days.

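### The declared secondary endpoint, the rate of z-score CAD at 2 and 6 weeks, has no between-group test or assigned patient-level rule in Section 7, whose coronary change analyses are set at weeks 1 and 5 instead of the scheduled day 14 and day 44 echocardiograms

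*Combined protocol and SAP*

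**What the plan says.** Section 2, Secondary Aim 2, asks whether etanercept "alters the rate of coronary artery dilation and disease (CAD) defined by z-scores at 2 and 6 weeks after treatment". Section 3.2 repeats it: "alters the rate of coronary artery disease defined by z-scores at 2 and 6 weeks after treatment". Section 3.2 adds two related questions. One is whether treatment "alters development of coronary artery dilation or disease in patients with normal coronaries on initial echocardiogram"; the other is whether it promotes healing of disease present at the start.

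The schedule in Section 6 puts echocardiograms at time 0, day 14 and day 44, and Sections 6.4 and 6.5 agree. Time 0 is the first dose of study drug. The day 7 visit has no echocardiogram. Under Section 6.7, Z-scores "will be determined for the left main coronary artery, proximal left anterior descending, and proximal right coronary artery", with a single central reader.

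Section 7 plans three things for the coronary data:

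- Summaries of Z-score and diameter, with changes from baseline "summarized for the post-treatment time points (week 1 and week 5) as well". Changes are also split by "whether or not the subject has evidence of dilation at baseline", meaning Z ≥ 2.5.
- A GEE on change values with terms for baseline dilation and its interaction with treatment. Its stated reason: "The GEE model is needed to accommodate adjustment for the correlation between observations obtained on the same individual at 1 and 5 weeks".
- An aneurysm analysis by Japanese criteria: "Comparison of post-treatment aneurysm proportions will be done via a stratified Chi-square test", with strata for aneurysm at baseline.

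**The concern.** The endpoint is a rate, so it needs a rule for when a patient counts as having CAD and a test of the resulting proportions. Section 7 gives neither. The two comparisons it does make answer other questions. A mean change in Z can move without patients crossing 2.5, and an aneurysm by Japanese criteria is a local diameter ratio of at least 1.5, not a Z-score. The definition and the test would then have to be chosen after data exist.

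The week labels are a smaller error in the same sentences. They name time points at which no echocardiogram is scheduled.

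Section 3.1 makes coronary measures secondary on purpose, so nothing here touches the primary analysis. But Section 1.1 gives reduction of coronary dilation as a primary goal of therapy, so readers will look for this result.

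**Working it through.** **1. Is the declared rate compared anywhere?**

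| Declared (Sections 2 and 3.2) | Group comparison in Section 7 |
|---|---|
| Rate of CAD by z-score, 2 and 6 weeks | None named |
| New CAD in patients normal at baseline | GEE on change, via the dilation-by-treatment interaction |
| Healing of CAD present at baseline | The same GEE interaction |
| (Aneurysm, listed in Section 7) | Stratified chi-square |

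**2. Is there a patient-level rule?** The cut-off is always Z ≥ 2.5, but its use differs.

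| Place | Purpose | Vessels | Aneurysm counts? |
|---|---|---|---|
| Section 4.1 | Eligibility in incomplete disease | Proximal coronary artery or left anterior descending | Yes |
| Follow-up Echocardiogram Surveillance | Trigger at visit 5 for data collection to 14 months | Not named | Yes |
| Section 7 | Baseline dilation | LMCA, pLAD and pRCA measured; no any-vessel rule | Not mentioned |

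The surveillance section does give a per-patient positive echocardiogram, but for another purpose. Section 7 also moves from dilation of the subject to dilation of the artery.

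**3. Timing, counted from first dose.**

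- Day 14: 14/7 = week 2.0; window days 11 to 17, weeks 1.6 to 2.4.
- Day 44: 44/7 = week 6.3; window days 40 to 48, weeks 5.7 to 6.9.
- Week 1 is day 7, and 11 − 7 = 4 days before the first window opens.
- Week 5 is day 35, and 40 − 35 = 5 days before the second opens.

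Other origins: from the day 14 dose, the echocardiograms fall at weeks 0 and 30/7 = 4.3, which does not fit. From the day 7 visit they fall at 7/7 = 1.0 and 37/7 = 5.3, which would round to 1 and 5. But Section 6 fixes time 0 at the first dose, and no section uses a day 7 origin.

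**4. What the missing test could show (context, not a measure of the defect).** Assumptions: two-sided 5%, 1:1 allocation of 196 (98 per group), and a control rate of 18.9%, the 6-week figure cited in Section 1.1. With p̄ the mean of the two rates,

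power = Φ{ [|p₁ − p₂| − 1.96·√(2p̄(1 − p̄)/n)] / √[(p₁(1 − p₁) + p₂(1 − p₂))/n] }.

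- 18.9% vs 9.45%: (0.0945 − 1.96 × 0.0498)/0.0494 = −0.064, power 47%. With the 110 per group of Section 2, 52%.
- 18.9% vs 5.8%: (0.131 − 1.96 × 0.0470)/0.0461 = 0.844, power 80%.

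Simulation of 20,000 trials per scenario, with 15% or 30% dilated at baseline and correlation 0.5 or 0.8 with follow-up (all assumed), supports stratifying by baseline status. Type I error stays near 5%, and power for the halving is about 49 to 61%, against 47 to 49% unstratified.

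**5. Continuous baseline Z in the GEE (optional).** For one artery at one visit, let ρ be the baseline to follow-up correlation, r the ratio of follow-up to baseline SD, and v the share of baseline variance left within the two dilation groups. Adding baseline Z to the dilation term raises effective sample size by

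gain = v(1 − ρr)² / [r²(1 − ρ²)].

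Assume baseline mean 1.0 to 1.4 and SD 1.2 to 1.4. Then v = 0.49 to 0.65.

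- r = 1, ρ = 0.3: 0.538v = 27 to 35%. r = 1, ρ = 0.9: 0.053v = about 3%.
- r = 1.2, ρ = 0.8: 0.003v = 0.2%.
- r = 0.8, ρ from 0.3 to 0.9: 28 to 64%.

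**The case against.** The strongest reply is that the coronary data are far from ignored and the intention is easy to see. Much of this stands, and it limits the point.

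- A reader might infer that coronary outcomes are not compared at all. Section 7 compares them twice; only the declared rate goes untested.
- A reader might infer that new CAD and healing have no analysis. Section 3.2 does not ask for proportions there, and the GEE interaction addresses both subgroups on a continuous scale.
- A reader might infer that the protocol has no notion of CAD. The 2.5 cut-off is used consistently. The open choices are the vessels and aneurysm, plus a sentence tying the rule to the endpoint.
- A reader might infer that the false-positive rate is 9 to 10%. Under no effect, with assumed correlations of 0.5 to 0.8, taking the better of the two visits gives about that. This is ordinary two-visit multiplicity. Both visits are declared, and nothing in the documents says that the better one will be reported.
- A reader might infer that baseline echocardiograms will often be missing. Section 6 schedules one at time 0 and Section 6.1 says it is performed. The schedule's notes make the baseline laboratory tests and EKG optional, but not the echocardiogram.

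The visits meant by weeks 1 and 5 are fairly clear, since only two post-baseline echocardiograms are scheduled. The labels still contradict Sections 2, 3.2 and 6. None of these replies supplies the missing test or assigns a rule to the endpoint.

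**Conclusion.** The point holds and should be fixed. Read literally, Section 7 never compares the declared rate of z-score CAD between groups, and it places the change analyses at times that match no scheduled echocardiogram. These conclusions come from setting the sections side by side and need no outside figure.

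The echocardiogram schedule agrees with the declared 2 and 6 weeks; it is the Section 7 labels that do not. The power figures rest on the cited 18.9% rate and equal allocation. They show that a negative result on this endpoint would say little unless the effect were large, which is no reason to leave it without a test. The GEE gain rests on assumed correlations and SDs and may be near zero. Omitting the covariate causes no bias, so that item is not an error correction.

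**What to change.** In Section 7:

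1. Replace the week 1 and week 5 labels, in all three places, by the day 14 (±3) and day 44 (±4) echocardiograms.
2. State that a patient has CAD at a visit if the centrally read Z-score is ≥ 2.5 in any of LMCA, pLAD or pRCA. Say explicitly whether aneurysm also counts, as it does in Section 4.1 and in the surveillance section. Use the same rule for baseline status, so that a patient with a baseline aneurysm is not classed as normal.
3. Compare the proportions with CAD at day 14 and at day 44 by a chi-square test stratified by baseline status, the form already used for aneurysm. Keep any patient without a baseline echocardiogram as a separate stratum. Report the strata separately, to supplement the GEE interaction on new CAD and healing. Naming one visit as the lead comparison is optional.
4. Separately, as a precision gain, add the same artery's continuous baseline Z-score to the Z-score GEE. Keep the dilation term and its interaction with treatment.

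The cost is analysis wording only. All three arteries are already read centrally, and no visit, echocardiogram or patient is added.
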